- e. Answering a survey to gather demographic information and information about recent exposures that might affect the results of the urine results and information about their participation in the fire

The results of the biological samples may tell us if sauna post-fire rehab is an effective means for increasing the body's removal of toxic chemicals during post-fire rehab with less than a 102 degree core body temperature increase.

3) Lay Summary (approximately 400 words)

The fire department chosen is a career fire department with approx. 260 active firefighters on staff. They respond to fire incidents and other medical emergencies in a 184 square mile area. They train recruits to become firefighters and annually proving drill training in various skills, such as live fire training. Following live fire responses (including training fires) their standard operating procedure includes a rehabilitation requirement to insure that no firefighter will be permitted to continue emergency operations beyond safe levels of physical or mental exertion (rehab).

They would like to add the use of a sauna post-fire response to their rehab SOP and have supported the UA study team lead by [name] to compare a chemical commonly excreted after firefighting to compare the value of adding sauna to rehab post-fire and monitoring the heart rate and temperature using a core body temperature/heart rate monitor data recorder. Urine will be collected for 12 hours immediately before the scheduled training fire and for 12 hours afterwards.

The core body temperature/heart rate monitor works by having the firefighter swallow a sensor shaped like a pill that the data recorder senses the temperature. The pill passes thru the gut and is removed with bowel movement, approximately in 24 hours, depending on the normal excretion timing of the person. A Polar heart rate belt that is worn around the body in the chest area and records the heart rate/pulse of the person wearing it. The firefighter will swallow the sensor and put on the Polar heart rate belt and the UA study team will start the data recorder before the firefighter enters the training fire and will continue to wear it for up to 8 hours afterwards.

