The study will seek participation from the fire department firefighters assigned or soon to be assigned to a training fire exercise. To test the best type of training fire exercise (flashover or burn room) we will need four for each group; this is referred to as Stage 1 in section 1, page 3 of this document. They may be the same firefighters or different, depending on the fire department schedule and the firefighters consent preferences.

After the training fire type is chosen (flashover or burn-room) up to 24 firefighters already scheduled to participate in a training fire as part of their continuing education will be selected as participants in the study exercise referred to as Stage 2 involving urine collection, skin wipes, core body temperature monitoring, survey collection, etc. They will be selected based on the availability of the UA study team to be present during their training fire exercise and their consent preferences. This group of 20-up to 24 firefighters may consist of the same firefighters who participated in the Stage 1

fire(s) or may be different, depending on the fire department training fire schedules and the firefighters consent preferences.

The fire department employees can be included in the study if they:

- 1) Are employed as an active fire responder by the fire department
- 2) Are scheduled for a training fire exercise by the fire department in the next year.
- 3) Are currently a non-smoker (including cigarettes, cigars and e-cigarettes)
- 4) Cannot have any contraindications to the core temp pill, which are:
 - a. Do you weigh less than eighty (80) pounds?
 - b. Do you have any known or suspected obstructive disease of the gastrointestinal tract, including but not limited to diverticulitis and inflammatory bowel disease?
 - c. Do you exhibit or have a history of disorders or impairment of the gag reflex?
 - d. Have you had a previous gastrointestinal surgery?
 - e. Do you have any diseases or disorders of the esophagus?
 - f. Will you be undergoing Nuclear Magnetic Resonance (NMR) or MRI scanning less than 3 days after swallowing the sensor?
 - g. Do you have a low motility disorder of the gastrointestinal tract including but not limited to ileus?
 - h. Do you have a cardiac pacemaker or other implanted electromedical device?
 - i. Do you have a swallowing disorder? (problems swallowing)

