In order to insure we have enough firefighters consented for the scheduled training fires, we will plan to consent more than 24 firefighters, requesting approval for up to 40 firefighters. There is no power analysis planned for the recruitment of the firefighters.

7) Recruitment Methods and Consenting Process

a. Recruitment Process: We will recruit using a recruiting flyer that may be distributed at the fire department's main office, stations, newsletters, and list-serves.

b. Informed Consent:

We will consent firefighters, individually, who are interested in participating in a private area prior to the training fire exercise. Consent will be a written version, signed by the firefighter and administered by the UA study team who are well versed in the proper consenting process. The consenting process may be over the phone to facilitate urine collection prior to the training day. If consent is obtained over the phone, a signature will be obtained, in person, prior to the firefighter turning in the urine sample, or otherwise participating in any part of the research. Each page of the consent form will be individually discussed with the firefighter and will provide the firefighter with an opportunity to ask questions. Coercion and undue influence will be avoided by ensuring the voluntary nature of this study is stressed. Additionally, no supervisors will be involved in the consenting process.

As a condition of employment, all fire department firefighters are adults, fluent in English so all information and consenting materials will be presented in English. Only non-smoking firefighters (including cigarettes, cigars and e-cigarettes) will be recruited, to minimize smoke exposure not associated with live-fire training.

8) Research procedures involved in the Human Research

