Stage 1: An initial four firefighters will be evaluated for change in PAHs associated with standard fire department flashover training to determine if urinary PAH metabolites increase following exposure, comparing baseline urine samples before training to a repeat sample collected after cessation of training. If a significant increase is not seen, then repeat testing with four additional firefighters will be completed using alternate burn room training fire. Prior to starting the training fire, the subjects will provide a 12-hour pre-fire urine sample, swallow a core temperature probe and wear a monitor and heart rate belt for recording both their core temperature and heart rate. In addition, dermal wipes will be collected prior to the training fire. Firefighters may wear a personal air monitor to capture the quality of the air during the training exercise. Post-fire dermal wipe samples will be collected after the firefighter removes turnout gear. Post-fire 12 hour urine samples will be collected in the same manner as the pre-fire urine samples. Subjects will also be asked to complete the exposure assessment survey. Specific procedures as explained in more detail below.

Stage 2: Once a measurable increase in post-fire urinary PAH has been documented, the associated training fire (flashover training or burn room training), testing will be carried out in up to 24 subjects.

Urine, core temperature, heart rate, dermal wipe and air monitoring samples will be collected as in Stage 1 collection.

In addition, following the standard rehab, the firefighters will be randomly selected to either saunatreatment or no additional treatment as explained in the "Sampling Protocol Timeline" below.

The Sampling Protocol Timeline for the Stage 1 and Stage 2 training fires:

- 1. Beginning of sampling period: The UA study team will meet each firefighter at the training fire facility prior to beginning their training fire. Firefighters will have already been consented and their contraindications forms completed at an earlier date as described in the "Informed Consent" and "Risks to Subjects" sections. The UA study team will read the contraindicated form to the participant one more time to confirm that they have not experienced any of the contraindications. If they answer 'yes' to any of the contraindications, they will be excluded from the study. If the firefighter consented by phone, the consent form will be signed by the firefighter before continuing.

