 - 8. **(For Stage 2 fires only)** The subjects will then be randomized to either an infrared sauna treatment, or no additional treatment following their fire department protocols. The firefighters will be randomized by the UA study team as such: Firefighters will pull a piece of paper out of a helmet; if it says "sauna" they will participate in the sauna treatment. If it is blank, they will participate in no additional post-fire treatment. "Sauna treatment" consists of a firefighter entering the sauna for 20 minutes as soon as the fire department has completed their standard rehab.
 - 9. Following the sauna treatment or no additional treatment time period, dermal wipes of the left calf, arm, and neck will be repeated and the subjects will complete a survey and return to work. The dermal wipe samples will be transported under Arizona Department of Transportation guidelines for transportation of samples to the University of Arizona.
 - 10. Core temperature and heart rate will continue to be monitored for up to 8 hours after training scenario. At the end of the 8 hour period, the firefighter will turn the monitor off by pressing the "stop" button and the "On/Off" button.
 - 11. The subjects will collect all their urine after the fire training for a period of up to 12 hours in the same manner that urine was collected prior to the fire training.
 - 12. End of sampling period: At the end of the sampling period, the UA study team will, again, meet the firefighters at the fire department to collect the data recorder/heart rate monitor data recorder, Polar Heart Rate belt, and urine samples.
 - 13. The urine will be stored at the Medical Research Building at -80 deg C until analyzed for urinary PAH metabolites and potentially other toxicants from the fire, and, dependent on the available budget, similar evaluations may be carried out on the skin wipes. The core

temperature and heart rate data will be downloaded from the data recorder onto a password protected computers and will be analyzed for comparison to the pre-fire data. The personal air monitors will be downloaded in the same manner and analyzed for air quality.

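### No fire-free interval or deferral rule protects the 12-hour baseline urine, so a recent fire can raise the baseline and mask the PAH rise, chiefly in the four-person Stage 1 decision

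*Protocol*

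**What the plan says.** **Who enters.** Protocol section 6 (Study Population) requires that participants "Are employed as an active fire responder by the fire department". None of the four inclusion criteria mentions time since the last fire. Section 3 (Lay Summary) says of the department: "They respond to fire incidents and other medical emergencies in a 184 square mile area".

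**Which competing exposure is controlled.** Only smoking. Section 7b gives the reason for recruiting non-smokers: "to minimize smoke exposure not associated with live-fire training".

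**The baseline.** Section 3: "Urine will be collected for 12 hours immediately before the scheduled training fire and for 12 hours afterwards". In the section 8 timeline, step 1 re-reads only the contraindications to the temperature pill, and step 3 accepts the urine. Neither step asks about a recent fire.

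**The survey.** Section 2, objective e, includes recent exposures that could affect the urine results. Section 3 describes the instrument as post-fire. Step 9 places it after the fire, the draw and the sauna or no-treatment period: "the subjects will complete a survey and return to work".

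**What depends on the change.** Stage 1 (section 8) tests four firefighters after flashover training, "comparing baseline urine samples before training to a repeat sample collected after cessation of training". If no significant increase is seen, four more are tested with burn-room training. Stage 2 starts once a measurable rise has been documented. Section 6 adds that the Stage 2 group "may consist of the same firefighters who participated in the Stage 1" fires, and states no minimum interval.

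**The concern.** The Protocol recognises that smoke from elsewhere can reach the urine, and it removes one source by excluding smokers. The obvious occupational source, a recent incident or another training fire, is left open. A firefighter who attended a fire on the previous shift, or during the 12-hour collection itself, is sampled as planned and that urine becomes the baseline.

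Metabolites still being excreted from the earlier fire add more to the pre-fire collection than to the post-fire one, so the observed change is smaller than the true change. With four people per test, one or two such baselines could turn a real rise into a non-significant one and send the study to burn-room fires for the wrong reason. A later analysis can exclude or flag such a person, but it cannot recover a clean baseline, and losing one of four is expensive.

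**Working it through.** The Protocol states no half-life, effect size, SD or power (section 6 says no power analysis is planned), so there is no figure of its own to reproduce. Every kinetic and variance input below is an assumption. From the Protocol come the 12-hour windows before and after the fire, n = 4 in Stage 1, and up to 24 in Stage 2, half of them to sauna (taken as 12 per arm).

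**1. Loss of the within-person rise.** Assume first-order excretion with k = ln 2 / half-life, and an earlier fire of relative dose d ending t hours before the baseline window. In units of the training-fire dose:

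- Pre = d·e^(−kt)·(1 − e^(−12k))
- Post = (1 − e^(−12k))·(1 + d·e^(−k(t+12)))
- Observed rise / true rise = 1 − d·e^(−kt)·(1 − e^(−12k))

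| Earlier fire | half-life 5 h | 10 h | 20 h |
|---|---|---|---|
| d = 1, t = 0 | 19% | 44% | 66% |
| d = 1, t = 12 h | 85% | 75% | 78% |
| d = 1, t = 48 h | 100% | 98% | 94% |
| d = 2, t = 0 | −62% | −13% | 32% |

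The severe figures need a fire ending just as collection starts. The negative ones also need double the dose.

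**2. Loss on the ratio scale.** Add a background excretion of 1 and a clean post/pre ratio R. Let h be the half-life, g the gap from an equal earlier fire to the start of the baseline window, and f(t) = 2^(−t/h) − 2^(−(t+12)/h), the fraction excreted in a 12 h window starting t hours after a fire. Set A = (R − 1)/f(0). Then Pre = 1 + A·f(g) and Post = 1 + A·f(0) + A·f(g+12).

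Example with R = 3, h = 12, g = 12: f(0) = 0.5, A = 4, f(12) = 0.25, f(24) = 0.125. Pre = 2.0, Post = 3.5, observed ratio 1.75 instead of 3.

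| Observed ratio when R = 3 | g = 12 h | 24 h | 48 h | 72 h | 7 days |
|---|---|---|---|---|---|
| h = 12 h | 1.75 | 2.17 | 2.72 | 2.92 | 3.00 |
| h = 24 h | 1.66 | 1.85 | 2.24 | 2.54 | 2.96 |

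**3. Stage 1 power.** The Protocol does not name the test. Assume a paired t-test on log ratios, n = 4, two-sided 0.05, log-ratio SD 0.4, h = 12 h. With R = 3 and nobody exposed, the standardised change is ln 3 / 0.4 = 2.75 and power is 94% (noncentral t). With exposed firefighters (simulation):

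| R = 3, gap | 1 of 4 exposed | 2 of 4 | 4 of 4 |
|---|---|---|---|
| 12 h | 77% | 60% | 48% |
| 24 h | 87% | 81% | 73% |
| 48 h | 93% | 92% | 90% |

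With R = 2, clean power is 64%, falling to 51%, 41% and 29% at a 12 h gap.

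**4. Aim 1 in Stage 2.** The helmet draw at step 8 comes after the baseline urine and the fire, so prior exposure is balanced between arms in expectation and the expected bias is zero. If a fraction q had a fire 12 h before baseline (h = 12 h, R = 3), the shift in their log change is D = ln 3 − ln 1.75 = 0.539, and the SD becomes √(0.4² + q(1 − q)D²). The minimum detectable log difference at 80% power is SD × √(2/12) × (1.960 + 0.842).

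| q | SD | increase | detectable difference |
|---|---|---|---|
| 0 | 0.400 | – | 0.457 |
| 2/24 | 0.427 | 7% | 0.488 |
| 0.10 | 0.431 | 8% | 0.493 |
| 0.50 | 0.482 | 21% | 0.552 |

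Across R = 2 to 3, SD 0.4 to 0.6 and q from 10% to 50%, the SD rises by 1% to 21%.

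**The case against.** Several points on the other side stand.

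- A reader might infer that carry-over will occur. The Protocol does not support that: it gives no call frequency, shift pattern, half-life or relative dose, and many of the calls are medical. About 260 firefighters share them. The risk is open, but its frequency is unknown.
- A reader might infer that carry-over hides the sauna effect in Aim 1. It does not do so systematically. Aim 1 compares arms allocated after baseline, so the cost is variance and possible chance imbalance. One or two exposed people among 24 add a modest amount under the inputs used here.
- Reuse of Stage 1 firefighters in Stage 2 looks like a main route of contamination, but is a minor one. A Stage 1 urinary rise must be documented first, so samples have to be analysed between the stages. At a gap of 7 days the modelled baseline inflation is at most 3% (half-life up to 24 h, clean ratio up to 5). No minimum gap is written, but nothing points to one of a day or two.
- The Protocol does anticipate earlier exposure through the survey, and section 4 speaks of surveys before and after the fire, which leaves the timing less settled than step 9 suggests. How the answers enter the analysis is a matter for a SAP, and its absence here is no fault.
- A false negative for flashover leads to four more firefighters in a burn room, not to loss of the pilot.

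What remains is the sampling-day rule. Section 3 and step 9 both put the exposure question after the fire, and no procedure defers anyone on the basis of it. A SAP cannot supply that afterwards.

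**Conclusion.** The point holds in a limited form and should be fixed before sampling. As written, the procedures can accept a baseline contaminated by a recent fire, although the Protocol itself treats non-training smoke as something to minimise.

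The exposure that matters is a fire within roughly the day before collection starts, or during collection. Under the stated assumptions, one or two such firefighters out of four lower Stage 1 power from 94% to 77% or 60% at a 12 h gap; at 48 h with a 12 h half-life the loss is small. For Aim 1 the consequence is an SD increase of 1% to 21% over the scenarios tried, with no expected bias. All sizes depend on assumed half-life, dose, ratio and SD. How often a recent fire would occur cannot be judged from the Protocol.

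**What to change.** Add one sampling-day condition to section 6: no live-fire, overhaul or training-fire exposure for a fixed period before the 12-hour collection starts, and none during it. The sponsor should justify the period from the half-life of the metabolites it will measure. A period of 48 h is only an example; on the ratio scale, assumed half-lives of 12 to 24 h point to about 3 to 7 days.

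Ask the question when the collection is arranged, and again at step 1 when the contraindication form is re-read. Move anyone who fails to a later session. As a minor addition, apply the same interval between study fires for any firefighter who is used more than once.

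The cost is one eligibility line, one question and some rescheduling. Consenting up to 40 for up to 24 Stage 2 places leaves 40 − 24 = 16 spare. If both Stage 1 groups are different people and count towards the 40, the margin is 16 − 8 = 8. A longer interval will defer more people, so the period should be no longer than the half-life requires.

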- 2. If the firefighter answered 'no' to all contraindications, the UA study team will instruct the firefighter to swallow the core thermo pill (the sensor will pass through the body and excreted with their normal bowel movement at the subject's normal rate of motility, which is typically 24-36 hours).
- 3. The UA study team will accept the urine sample collection the firefighter began collecting approximately 12 hours before the anticipated start of the fire. If one of the 12 hour urine samples has not yet been collected by the firefighter, a "zero" hour baseline sample will be collected at the time of the scheduled training.
- 4. The Polar heart rate belt will be donned by the firefighter and three dermal skin wipes (calf, arm, and neck) will be collected prior to the firefighter donning the turnout gear.

- 5. When the fire department personnel say that it is time for the firefighter to don their turnout gear, the UA study team will turn on the core body/heart rate monitor data recorder. Next, the UA study team will place the core body/heart rate monitor data recorder in the firefighter's inner pocket of their turnout jacket. The UA study team will make sure the data is recording by pressing the "run" button to see that it registers a digital reading. After the firefighter is in full gear, the placement of the heart rate monitor/data recorder will be accessed for firefighter activity safety (not impeding movement) and a personal air monitor may be attached to the outside of the turnout gear jacket in an unobtrusive location.
- 6. The firefighter will enter the training fire room as instructed by standard fire department protocol for the standard period of time for participation in the training fire. Following cessation of the training fire, the subjects will follow their standard fire department procedures for post-fire treatment (rehab).
 - 7. The UA study team will remove the personal air monitor from the firefighter's turnout jacket (if applicable). The firefighters will remove their turnout gear at this time. The heart rate/core body temperature monitor data recorder will be transferred from the turnout jacket inner pocket to a pants pocket. A dermal wipe (a gauze pad moistened with alcohol) of the left calf, arm, and neck will be obtained prior to cleaning their skin with their standard rehab baby wipes (part of the standard fire department procedures for post-fire treatment.)

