We would like to take pictures during the activities such as wearing the monitors, performing skin wipes, going into or coming out of the training fires or sauna, including cleaning up gear, for possible use in manuscripts, presentations, posters, and/or brochures to present a visual description of the activities involved in the training fire study. The subjects will be asked to agree or decline being in photos.

Specific Sampling Protocols for Stage 1 and Stage 2 training fires:

Urine sampling: before and after the fire:

For each urine sample collected, the total amount of each voided sample will be collected in a 200ml sample collection container and stored in an ice chest until picked up by the UA study team. The subjects will collect all their urine after the fire training for a period of up to 12 hours in the same manner as they collected their urine prior to the fire training.

Core body/heart rate monitoring before and after the fire:

The monitor that records their core temperature and heart rate is a small instrument, approximately the size of a double deck of playing cards $(3/4" \times 1 \%" \times 4 \%")$ in a fabric protective pouch that can be worn on a belt or placed into a jacket pocket. The monitor will be turned on before the firefighter enters the training room fire and not turned off until up to 8 hours after the fire.

The heart rate belt is a 3/4"strap (T31 Polar Transmitter) that is worn around the body in the chest height area. It will be donned by the firefighter before the monitor is turned on and not removed until the monitor is turned off.

Monitoring of the core body temperature and the heart rate by the UA study team begins before the fire and continues for up to 8 hours after the fire so that a comparison between the standard post-fire and the sauna post-fire methods can be compared for core body temperature return to normal and heart rate return to normal.

Dermal wipes: before and after the fire:

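### No step has every firefighter empty the bladder before the fire, so some pre-fire urine can be counted as post-fire urine in the PAH comparison

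*Protocol*

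**What the plan says.** All references are to the Protocol.

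- **Baseline collection (section 8, Sampling Protocol Timeline, step 3).** "The UA study team will accept the urine sample collection the firefighter began collecting approximately 12 hours before the anticipated start of the fire". The window is timed to the expected start, not the actual one. The same step then adds: "If one of the 12 hour urine samples has not yet been collected by the firefighter, a 'zero' hour baseline sample will be collected".
- **Between hand-over and fire entry (steps 4 to 6).** Heart rate belt, three skin wipes, turnout gear, recorder set-up, entry. No void is mentioned.
- **Post-fire collection (step 11).** "The subjects will collect all their urine after the fire training for a period of up to 12 hours". The urine sampling paragraph of section 8 repeats this and has each void collected whole: "For each urine sample collected, the total amount of each voided sample will be collected in a 200ml sample collection container". The first void after the fire is neither set aside nor treated separately, and void times are not asked for.
- **Labelling (section 12).** Urine is identified by subject number and by baseline or post-fire status only.
- **Intended window (section 3, Lay Summary).** "Urine will be collected for 12 hours immediately before the scheduled training fire and for 12 hours afterwards".
- **Use of the data (section 8, Stage 1).** The comparison is within person, "comparing baseline urine samples before training to a repeat sample collected after cessation of training", in four firefighters. It drives a decision: "If a significant increase is not seen, then repeat testing with four additional firefighters will be completed using alternate burn room training fire". Stage 2 starts once a measurable post-fire increase has been documented.

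**The concern.** A timed urine collection is bounded by voids. To divide pre-fire from post-fire urine at the fire, the bladder should be emptied just before it. Here that happens by rule only for someone who still owes a baseline sample. For anyone else the dividing line is the last void they happened to make. Urine formed between that void and fire entry belongs to the baseline period, but it is passed after the fire and labelled post-fire.

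Urinary PAH metabolites are the Aim 1 outcome in section 2. In Stage 1 the pre-to-post change in four people decides whether flashover training is kept or burn room training is tried. With so few people, dilution of the change and avoidable variation between persons both count. Once mixed in the bladder, the two kinds of urine cannot be separated by any later analysis.

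**Working it through.** The protocol gives no figure to reproduce: it states no effect size, SD or alpha, and section 6 says "There is no power analysis planned for the recruitment of the firefighters". The size below is an illustration.

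**Inputs**
- From the protocol: post-fire collection of up to 12 h, taken as 12 h; baseline window of about 12 h.
- Assumed, not in the protocol: T = 0.5 to 3 h from last pre-fire void to fire entry; fire of 0.5 h; constant urine flow; concentration changes by a true factor R from fire entry onward; R = 2.0 for the example.

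**1. Concentration, pooled post-fire urine**

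Pre-fire share f = T / (T + 0.5 + 12). Observed ratio = f + (1 − f)R, which is 2 − f when R = 2.

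| T (h) | f | Observed ratio, true 2.0 |
|---|---|---|
| 0.5 | 0.5/13 = 3.8% | 1.96 |
| 1 | 1/13.5 = 7.4% | 1.93 |
| 2 | 2/14.5 = 13.8% | 1.86 |
| 3 | 3/15.5 = 19.4% | 1.81 |

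For any R, the excess over 1 shrinks by the factor 1 − f. The same true rise therefore reads differently from person to person, according only to when each last voided.

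**2. Concentration, first post-fire void alone**

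If that void comes t = 0.5 to 2 h after the fire, the share is T / (T + 0.5 + t).
- Smallest: 0.5 / (0.5 + 0.5 + 2) = 17%, and a true 2.0 reads 1.83.
- Largest: 3 / (3 + 0.5 + 0.5) = 75%, and a true 2.0 reads 1.25.

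**3. Amount excreted, no fire effect**

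Three boundaries now matter. Let S be the hours of urine already in the bladder when the baseline starts, T as above, and E the hours left in the bladder when the post-fire collection ends.

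Post/pre ratio = (12.5 + T − E) / (12 − T + S)

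- No carry-over anywhere: 12.5/12 = 1.04.
- S = T = E, any value: 12.5/12 = 1.04.
- T = 3, S = 0, E = 3: 12.5/9 = 1.39.
- T = 3, S = 3, E = 0: 15.5/12 = 1.29.
- T = 3, S = E = 0: 15.5/9 = 1.72.
- T = 0.5, S = E = 3: 10/14.5 = 0.69.

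The protocol fixes none of S, T or E, so on this scale the error can go either way or vanish.

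**4. With a void from everyone just before the fire**

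T is close to 0, so f is close to 0 and the observed concentration ratio is close to R.

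**The case against.** **Carry-over is possible, not established.** A reader might infer that firefighters who complied with the baseline collection enter the fire with pre-fire urine in the bladder, or that the plan deliberately sets two boundaries for two kinds of participant. The documents support neither. The Lay Summary runs the baseline up to the fire, nothing forbids a void before gearing up, and someone who voids then carries over almost nothing. This stands. What remains is that no operative step carries out the Lay Summary's intention for everyone.

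**A false rise in amounts.** It is tempting to quote the 1.72 above as a spurious increase. That needs an empty bladder both at the start of baseline and at the end of the post-fire collection, neither of which is stated. Section 8 has post-fire urine collected in the same way as pre-fire urine, and equal carry-over at all three boundaries gives 1.04, the value with no carry-over at all. This objection stands in full, and no false-rise figure should be claimed.

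**The pooled effect is small, and the analysis may be settled elsewhere.** Dilution of the pooled ratio is 2% to 10% (1.96/2.0 to 1.81/2.0). Pooling, handling of the first void, and concentration versus amount may belong to an SAP that is not at hand. The first part stands. The second stands only in part: an SAP could drop the first post-fire void, but that would also lose the earliest post-exposure urine, and it cannot separate what is already mixed.

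**The consequences are limited.** If a rise after flashover training is missed, four more firefighters are tested in the burn room. In Stage 2 the draw for sauna takes place after the fire, so carry-over is balanced between arms in expectation. A reader might infer a biased sauna comparison; the design does not support that.

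**Conclusion.** The point holds as a gap in the collection procedure. Followed to the letter, the protocol permits pre-fire urine to be counted as post-fire, by an amount that differs between persons and is not recorded.

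On concentrations the effect is toward no change: about 4% to 19% of a 12 h pool under the assumed void times, and more if early single voids are analysed. These figures rest on constant flow, a 0.5 h fire and an immediate, sustained change in concentration, none of which the protocol gives. On amounts, no direction or size can be claimed.

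The practical weight lies in the Stage 1 comparison in four firefighters. In Stage 2 the cost is noise and dilution. Severity is minor: this is a cheap improvement to a pilot, not a flaw that invalidates it.

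**What to change.** In section 8, step 3, make the zero-hour void unconditional in both stages. Every firefighter empties the bladder just before donning turnout gear. That void is kept, its time is recorded, and it counts as the last baseline sample. In step 11, state that the post-fire collection starts from that void.

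The change is a sentence or two of text, one more self-collected void per firefighter and a few minutes at a meeting that already takes place. A little pre-fire urine can still form between gearing up and entry, but that interval is short and the recorded time shows how long it was.
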